7.8. Visit (D2, W1, W2, W4, W8, W12 and W24)

Follow-up visits will take place 48h after the vaccination (D2) and eventually at week 1 (W1), 2 (W2), 4 (W4), 8 (W8), 12 (W12), 24 (W24) and 48 (W48) after vaccination. Participants will be assessed for local and systemic AE, interim history, physical examination, review and blood tests at these endpoints. Blood will also be taken for exploratory immunology purposes.

If a participant experience adverse events (laboratory or clinical), which the investigator (physician) determine necessary for further close observation, the participant may be admitted to the clinical facility of the enrolling center. Moreover, investigator can decide to perform additional medical examination if needed.

Participants who experience symptoms that are associated with COVID-19 including fever ≥ 37.5 °C and/or respiratory symptoms will be treated according to local guideline for suspect cases of COVID-19 until an infection with SARS-CoV-2 is not excluded by a molecular test. A test for detection of SARS-CoV-2 on respiratory sample will be carried out on all participants with fever ≥ 37.5 °C persisting for more than 48 hours at any time after vaccination. Participants with confirmed COVID-19 will be admitted to hospital until clearance of the infection.

Schedule of attendance is reported in Figure 9.

7.9. Participants restrictions

Subjects will be asked to adhere to the following study restrictions along their study participation, which are also listed and explained in the ICF:

- A. not to do strenuous physical exercise during 2 days before each visit
- B. To be in fasting condition (for at least 8 h) at each visit
- C. To avoid alcohol during the 24 hours before each visit

8. Investigational vaccine production

8.1. Manufacturing and Presentation

The GRAd-COV2 vaccine consists of the replication-deficient simian adenovirus vector GRAd32, containing a stabilized surface glycoprotein (S-protein protein) antigen of the SARS-CoV2 expressed from the strong CMV IE promoter. The following vaccinations will be given in this study:

1. GRAd-COV2 5×10^{10} vp
2. GRAd-COV2 1×10^{11} vp
3. GRAd-COV2 2×10^{11} vp

GRAd-COV2 is manufactured in A195 Formulation Buffer at a concentration of 2×10^{11} vp/mL. The drug product is filled into 3mL glass vials (supplied by Nuova Ompi Stevanato Group) with a 13 mm grey chlorobutyl rubber stopper and a 13 mm aluminium seal (supplied by West Pharmaceutical Services). The filled vials are supplied sterile. The containers and closures are tested for compliance with defined specifications. The vials are made from Ph Eur borosilicate Type 1 glass.

8.2. Supply and Storage

GRAd-COV2 has been formulated and vialled under Good Manufacturing Practice conditions at the ReiThera Srl Facility, Roma, IT. At ReiThera Srl the vaccine will be certified and labelled for the trial by a Qualified Person (QP) before transfer to the clinical site.

The vaccine is stored at nominal -80°C in a locked freezer, at the clinical site. All movements of the study vaccines will be documented in accordance with existing standard operating procedure (SOP). Vaccine accountability, storage, shipment and handling will be in accordance with relevant SOPs and forms.

8.3. Administration of Investigational Medicinal Products

The dosages of GRAd-COV2 to be used in this study are: 5×10^{10} vp (low dose), 1×10^{11} vp (intermediate dose) and 2×10^{11} vp (high dose). See the SOP for detailed information on the preparation, labeling, storage, and administration of the GRAd-COV2 investigational vaccine. For administration of the high dose, 1ml of GRAd-COV2 will be injected without dilution. For intermediate and low dose, the vaccine will be diluted in sterile saline solution to reach a final 1ml injection volume. Vaccine dilution will be performed by the site pharmacist on the same day of vaccine administration.

On vaccination day, GRAd-COV2 will be allowed to thaw to room temperature and will be administered within 1 hour of removal from the freezer. The vaccine will be administered intramuscularly into the deltoid of the non-dominant arm (preferably). Qualified medical personnel will wear gloves. All volunteers will be observed in the unit for 4 hours (± 10 minutes) after vaccination. During administration of the investigational products, Advanced Life Support drugs and resuscitation equipment will be immediately available for the management of anaphylaxis. Vaccination will be performed and the IMPs handled according to the relevant SOPs.

The study will be performed in accordance with Genetically Modified Organisms (Contained Use) Regulations (2001/18/CE). In order to minimize dissemination of the recombinant vectored vaccine virus into the environment, inoculation sites will be covered with a dressing after immunization. This should absorb any virus that may leak out through the needle track. The dressing will be removed from the injection site after 30 minutes (+15/- 5 minutes) and will be disposed as GMO waste by autoclaving.

9. Adverse event assessment and management

Safety will be assessed by the frequency, incidence and nature of adverse events and severe adverse events arising during the study.

9.1. Definitions

Adverse event (AE). (AE) is any untoward medical occurrence in a participant, which may occur during or after administration of the vaccine and does not necessarily have a causal relationship with the intervention. An AE can therefore be any unfavorable and unintended sign (including an abnormal laboratory finding), symptom or disease temporally associated with the study intervention, whether or not considered related to the study intervention.

Adverse reaction (AR). An AR is any untoward or unintended response to the vaccine. This means that a causal relationship between the vaccine and an AE is at least a reasonable possibility, i.e., the relationship cannot be ruled out. All cases judged by the reporting medical Investigator as having a reasonable suspected causal relationship to the vaccine (i.e. possibly, probably or definitely related to the vaccine) will qualify as adverse reactions.

Unexpected adverse reaction (UAR). An UAR is any untoward or unintended response to the vaccine, the nature and severity of which is not consistent with the information about the medicinal product in question set out in the investigator brochure (IB) or summary of product characteristics.

Serious adverse event (SAE). A SAE is an AE that results in any of the following outcomes, whether or not considered related to the study intervention.

- A. Death
- B. Life-threatening event (i.e., the participant was, in the view of the Investigator, at immediate risk of death from the event that occurred).
- C. Persistent or significant disability or incapacity (i.e., substantial disruption of one's ability to carry out normal life functions).
- D. Hospitalization, regardless of length of stay, even if it is a precautionary measure for continued observation.
- E. Significant medical intervention including surgery or administration of drugs (examples of such medical events include allergic reaction requiring intensive treatment in an emergency room or clinic, blood dyscrasias, or convulsions regardless eventual need of hospitalization)
- F. A grade ≥ 3 abnormalities on safety blood test according to Common Terminology Criteria for Adverse Events (CTCAE v.4 and MedDRA 12.1).

Serious adverse reaction (SAR). A SAE (expected or unexpected) that, is in the opinion of the reporting Investigator, believed to be possibly, probably or definitely due to the vaccine.

Suspect unexpected serious adverse reaction (SUSAR). A severe adverse reaction, the nature and severity of which is not consistent with the information about the medicinal product in question set out in the investigator brochure (IB) or Summary of Product Characteristics.

9.2. *Solicited Adverse Reactions*

Solicited Adverse Reactions are those (foreseeable) AEs following vaccination with GRAd-COV2, and include injection site pain, erythema, warmth, swelling, pruritus, myalgia, arthralgia, headache, fatigue, fever, feverishness, malaise and nausea.

Solicited Adverse Reactions are grade as following:

- A. None: Symptom does not experience
- B. Mild: Short-lived or mild symptoms; medication may be required. No limitation to usual activity
- C. Moderate: Mild to moderate limitation in usual activity. Medication may be required but hospitalization is not required.
- D. Severe: Considerable limitation in activity. Invasive intervention or hospitalization is required.

We do not expect life threatening or fatal solicited adverse reactions in this study.

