4.2. Endpoints

4.2.1. Primary endpoints (safety)

The primary endpoint of the study is to assess safety in term of occurrence of solicited and unsolicited adverse events (AE). Occurrence of AE will be monitored by preplanned medical visits and blood tests (active surveillance) and by recording participant's reported AE (passive surveillance). This includes:

- A. Occurrence of solicited local AE signs and symptoms for 7 days following the vaccination
- B. Occurrence of solicited systemic AE signs and symptoms for 7 days following the vaccination

- C. Occurrence of unsolicited AE for 28 days following the vaccination
- D. Change from baseline for safety laboratory measures at different 2 days, 7 days, 2 weeks, 4 week, 8 weeks, 12 weeks and 24 weeks
- E. Occurrence of serious AE (SAE) during the whole study duration

Volunteers will undergo clinical follow up for AE for 24 weeks following completion of the vaccination regimen. SAEs will be collected throughout the study.

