9.7. Management of participants with AE

The clinical center that enroll participants will provide care to any participant with any AE as appropriate for the clinical conditions.

Each enrolling center will have a medical investigator that will ensure real-time safety oversight. The local medical investigator will review AEs deemed possibly, probably or definitely related to study interventions. The local investigator will immediately register AE and will notify them to principal investigator according to SOP. Moreover the local investigator can decide to place the study on hold if deemed necessary following a study intervention-related as severe or unexpected event such as: SAE, UAR, SAR and SUSAR. The decision to put the study on hold is immediately notified to principal investigator and to DSMB.

Table 1 Adverse event severity scale

Adverse events	Severity			
	None	Mild	Moderate	Severe
Erythema	no	3-50 mm	51-100 mm	>100 mm
Swelling	no	3-20 mm	21-50 mm	> 50 mm
Ulceration	-	-	-	any
Fever	36.0-37.4	37.5-38.0	38.1-39.0	>39.0
hypothermia		35.9-35.1	-	<35
Tachycardia (bpm)	55-100	101-115	116-130	>130
bradycardia (bpm)		50-54	40-49	≤40
Systolic hypertension	85-140	141-159	160-179	>179
Systolic hypertension		85-89	80-84	<80
Diastolic hypertension	<90	91-99	100-109	>109
Respiratory Rate low	12-20	-	9-11	<9
Respiratory Rate high		-	21-24	>24
SpO2 at FiO2 21%	>97	94-96	92-93	<92
Consciousness	Alert	-	-	any
Biochemistry	MedDra and CTAE. Grade 1-2=mild; Grade 3/4= severe/life threatening			
Blood counts				

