9.8. Halting rules and study termination due to safety issue

Safety halting rules have been developed considering the fact that this is a *first-in-human* dose escalation study. Solicited adverse events are those listed as in section 9.2, occurring within the first 7 days after vaccination (day of vaccination and six subsequent days). Unsolicited adverse events are AE other than the solicited AEs occurring within the first 7 days, or any AEs occurring after the first 7 days after vaccination.

Enrolment of participants in one arm will be upheld if:

- A. Solicited local adverse events (site of injection): 2 or more vaccinations in a group are followed by the same severe solicited local adverse event beginning within 2 days after vaccination (day of

vaccination and one subsequent day) and persisting at severe for >48 hrs and these are deemed possibly, probably or definitely related to study interventions.

- B. Solicited systemic adverse events: If 2 or more vaccinations in a group are followed by the same severe solicited systemic adverse event beginning within 2 days after vaccination (day of vaccination and one subsequent day) and these are deemed possibly, probably or definitely related to study interventions.
- C. Unsolicited adverse events: If 2 or more vaccinations in a group are followed by the same serious unsolicited adverse event (including the same laboratory adverse event) and relation with vaccination cannot be immediately excluded.
- D. One participant with serious adverse event considered possibly, probably or definitely related to vaccination occurs
- E. Life-threatening condition when relation with study intervention cannot be immediately excluded.
- F. Death when relation with study intervention cannot be immediately excluded.

If a halting rule has been met, we will inform the regulatory authority. Moreover, before restarting enrollment the DSMB should exclude that AE has no immediate causal relation with the vaccine or that benefit of vaccination outweigh risk of further AE occurrence. In these latter case Ethical committee should be involved in the decision. Halting rules apply to one dose and the next higher one, so that if halting rule is met for the highest dose, only this arm is upheld. If halting is met for intermediate dose, two arms are held. If halting rule is met for the lowest dose all the study is stopped pending on the investigation of causal association between AE and vaccination (DSMB advice).

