#### 4.11.1 Adverse Events

Adverse events (AEs) will be coded using the Medical Dictionary for Regulatory Activities (MedDRA) Version 23.0.

An AE is any untoward medical occurrence in a study subject administered an IMP which does not necessarily have a causal relationship with this treatment. An AE can therefore be any unfavorable and unintended sign (including a clinically significant abnormal laboratory finding), symptom, or disease temporally associated with the use of an IMP, whether or not considered related to the IMP. Adverse events may include the onset of new illness and the exacerbation of pre-existing conditions.

Other untoward events occurring in the framework of a clinical study will be recorded as AEs, e.g. those occurring during treatment-free periods (including Screening or post-treatment Follow-up periods), in association with study-related procedures and assessments or under placebo.

Concomitant illnesses, which existed before entry into the clinical study, will not be considered AEs unless they worsen during the treatment period. Pre-existing conditions will be recorded as part of the subject's medical history.

A treatment-emergent adverse event (TEAE) is defined as an AE that begins or worsens in severity in 28 days after study drug administration.

Adverse event with 'No Relationship' or 'Unlikely Related' causality will be evaluated as not related (relationship = No), otherwise (including missing causality) AE will be evaluated as related (relationship = Yes).

Adverse events with completely unknown start dates will be considered as treatment-emergent for the tabulations and will be shown as NK in the listings. Partially complete AE dates will not be imputed in the listings and the available day, month and year components will be used to determine if an adverse event is treatment-emergent taking the first dosing date and end of study date as references.

Solicited adverse reactions are foreseeable AEs following vaccination with GRAd-COV2 including the following AEs: injection site pain, erythema, warmth, swelling, pruritus, myalgia, arthralgia, headache, fatigue, fever, feverishness, malaise and nausea. Solicited adverse reaction is recorded as such on the corresponding AE's eCRF.

Adverse events of special interest (AESI) are any grade  $\geq 3$  abnormalities on safety blood test according to Common Terminology Criteria for Adverse Events v.5.0 (CTCAE, see section [4.11.3](#)).

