#### 4.11.3 Clinical Laboratory Evaluation

Safety laboratory evaluations (hematology, biochemistry and urinalysis) will be assessed as shown in the Schedule of Assessments (Appendix 6.1). For list of safety laboratory test parameters refer to Blood test and other analysis for monitoring safety (section 8.3) in study protocol.

Urinalysis results will be listed only.

Hematology and biochemistry results will be graded according to NCI CTCAE (Version 5.0). Individual CTCAE grades will be provided with the by-subject listings.

For each hematology and biochemistry parameter:

- Results and change from baseline will be summarized descriptively by visit and treatment group;
- Number and percentage of subject in normal range categories will be tabulated by visit and treatment groups.
- Number and percentage of subject in each CTCAE severity grades will be tabulated by visit (and overall) and treatment groups.

Worst post-baseline record will be selected (flagged) by utilizing the rules as follow:

If there is any LOW or HIGH record, flag the most extreme record. Most extreme record will be derived by using the factor (f) for corresponding normal limits as appropriate ( $f \times LLN$  or  $f \times ULN$ ). If there are multiple records with most extreme value, flag the earliest occurrence. If not out of normal range results is observed flag the first post-baseline observation.

By-subject listing of hematology and biochemistry with change from baseline will be provided by dose and time point for each treatment group separately.

All values outside the clinical reference ranges will be flagged in the data listings. The abnormal values will be flagged with 'L' for values below the lower limit of the clinical reference range and 'H' for values above the upper limit of the clinical reference range and included in the listings. The Investigator will assess whether the values outside the clinical reference range are clinically

significant (CS) and these will be reported as abnormal NCS or abnormal CS. Clinically significant laboratory values will be recorded by the Investigator as AEs.

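### Protocol and SAP differ on when an abnormal laboratory value is an adverse event, so the 28-day unsolicited AE rate depends on which text is followed, and the SAP does not declare the difference

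*Protocol*

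**What the plan says.** **Protocol.** Section 9.1 says an AE can be "any unfavorable and unintended sign (including an abnormal laboratory finding"; clinical significance is not mentioned. Section 9.6 has AEs judged partly from a review of the biochemistry and haematology results at every visit. Table 1 in section 9.7 puts laboratory results on the AE severity scale as "Grade 1-2=mild; Grade 3/4= severe/life threatening". Section 9.8 states "Unsolicited adverse events are AE other than the solicited AEs occurring within the first 7 days", and also counts any AE after day 7. Its halting rule C speaks of unsolicited events "including the same laboratory adverse event". Primary endpoint C in section 4.2.1 is "Occurrence of unsolicited AE for 28 days following the vaccination". Item F of the SAE definition in 9.1 covers blood-test abnormalities of grade 3 or higher.

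**SAP.** Section 4.11.1 has nearly the same AE sentence as the protocol, but with "including a clinically significant abnormal laboratory finding". Section 4.11.3 applies the condition: "The Investigator will assess whether the values outside the clinical reference range are clinically" significant, labels them CS or NCS, and "Clinically significant laboratory values will be recorded by the Investigator as AEs". No threshold for the label is given. Section 4.11.1 makes grade 3 or higher blood-test abnormalities AESI; the SAE definition in 4.11.2 does not mention them. Section 4.15 lists only the added liver analyses as a change.

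**The concern.** The same laboratory result can be an AE under one text and not under the other. Laboratory findings are not among the solicited reactions in Protocol 9.2, so they are unsolicited and bear on a primary endpoint. A reader of the final report could not tell which rule produced the AE rate, or compare it safely with a trial that used the other rule.

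The grade 3 or higher results raise a second problem. The SAP reports AESI through AE records: a row in the AE overview, a summary by system organ class and preferred term, and a flag in the AE listing. But 4.11.3 calls for an AE record when a value is clinically significant, and nothing says AESI are derived from the laboratory data. A grade 3 value marked NCS could therefore be absent from the AESI row, although Protocol 9.1 F makes it an SAE criterion.

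**Working it through.** The documents state no AE rate, abnormality rate or power, so there is no figure to reproduce. The size can only be bounded under assumptions.

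**Inputs from the documents**
- Arm size: 15 (Protocol section 5).
- Post-dose safety draws within 28 days: D2, W1, W2 and W4, so 4, or 3 if W4 (window ±2 days) falls after day 28 (Protocol Figure 9).
- Analytes: Protocol 7.3 itemises about 10 in biochemistry (sodium, potassium, albumin, ALT, ALP, total and fractionated bilirubin, creatinine, BUN, LDH). The full blood count is not itemised.

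**Assumed inputs**
- p: chance that a single result is out of range, 0.2% to 5%.
- a: share of participants with a non-laboratory unsolicited AE, 0.2 to 0.8.
- s: chance that a participant with an abnormal value has one called clinically significant, 0.1 to 0.9.
- a, q (below) and s are taken as independent.

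**Step 1. Chance q of at least one out-of-range value.** For 10 analytes and 4 draws, independence gives q = 1 − (1 − p)^40. Perfect correlation over visits gives q = 1 − (1 − p)^10. The last column is a Gaussian-copula simulation with 60% of the variance persistent within analyte and 10% shared within participant.

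| p | independent | fully correlated | simulated |
|---|---|---|---|
| 0.2% | 7.7% | 2.0% | not run |
| 0.5% | 18.2% | 4.9% | 14.2% |
| 1% | 33.1% | 9.6% | 25.5% |
| 2% | 55.4% | 18.3% | 43.3% |
| 5% | 87.1% | 40.1% | 74.1% |

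**Step 2. Gap between the two rules.** A participant changes status if there is no other unsolicited AE, at least one abnormal value, and none called clinically significant: gap = (1 − a) × q × (1 − s).
- Low end: (1 − 0.8) × 0.02 × (1 − 0.9) = 0.0004, about 0 points.
- High end: (1 − 0.2) × 0.87 × (1 − 0.1) = 0.626, about 63 points. This is for 10 analytes; with 15, q is 95.4% and the product is 0.8 × 0.954 × 0.9 = 0.687.
- Middle, q = 0.33 and a = 0.5: 0.1485 for s = 0.1, 0.0825 for s = 0.5, 0.0165 for s = 0.9.

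**Step 3. What a 10-point gap needs.** q must be at least 0.10 / [(1 − a)(1 − s)]: 14% for a = 0.2, s = 0.1; 22% for a = 0.5, s = 0.1; 40% for a = 0.5, s = 0.5; 56% for a = 0.8, s = 0.1. With s = 0.9 and a = 0.2 the bound is 1.25, so a 10-point gap is impossible there.

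**Step 4. Scale of one arm.** One participant is 1/15 = 6.7 points. Two participants with no other unsolicited AE, classified differently, are 2/15 = 13.3 points.

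**Step 5. Grade 3 or higher values, side by side.** No arithmetic applies.

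| Source | Status |
|---|---|
| Protocol 9.1 F | SAE criterion |
| SAP 4.11.1 | AESI, reported from AE records |
| SAP 4.11.2 | not in the SAE definition |
| SAP 4.11.3, marked CS | AE record made, so can reach the AESI row |
| SAP 4.11.3, marked NCS | no AE record called for; still in the CTCAE grade tables |

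**The case against.** The strongest reply is that this is a difference of wording, and that the tempting larger claims go beyond the documents. Much of that stands.

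- A reader might infer that the protocol makes every out-of-range value an AE. It does not: 9.1 says an AE can be such a finding, if unfavorable and unintended, and Table 1 grades AEs without defining them. Inclusion criterion 12 already separates out-of-range values from those that may matter clinically.
- A reader might infer a gap of tens of points. For example, 12 to 18 analytes with 95% ranges, fully correlated over visits, give 1 − 0.95^12 = 46% to 1 − 0.95^18 = 60% with an abnormal value. A 20% base rate then becomes 57% to 68%. None of these inputs is in the documents, and the result is not a lower bound. A fully persistent abnormality would usually pre-date dosing, whereas a treatment-emergent AE must begin or worsen afterwards. The sum also counts both tails of the reference range as unfavorable and assumes no value is called significant.
- The treatment-emergent tables include solicited reactions. If 80% of participants already have an event, q = 0.87 and s = 0.1 give only 0.2 × 0.87 × 0.9 = 15.7 points in that row.
- A reader might infer that the two centres record differently, or that the DSMB loses laboratory signals. Nothing shows the former. On the latter, SAP 4.11.3 tabulates out-of-range values and CTCAE grades whatever the label, 4.11.4 adds liver tables, and endpoint D covers laboratory change.
- The texts may belong to different versions. The SAP rests on Protocol Version 2.0, cites section 8.3 for safety blood tests that are in 7.3 here, and shows a 28-day screening window in its schedule against 21 days in the protocol.

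The reply does not remove the undeclared difference, its bearing on endpoint C, or the lack of a rule that brings an NCS grade 3 value into the AESI row.

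**Conclusion.** The point holds as an undeclared inconsistency that should be fixed. The protocol admits abnormal laboratory findings as AEs without a filter; the SAP adds an investigator judgement with no stated threshold. The effect on the unsolicited AE rate cannot be fixed from the documents. It is large only if isolated abnormalities are common, few are called clinically significant and other unsolicited AEs are not already frequent; otherwise it is a few points or less.

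The AESI gap is a separate, narrower defect: an incomplete AESI row is possible, but the value is not lost from safety reporting. All of this is subject to the wording of Protocol Version 2.0, which could not be confirmed as the text supplied.

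**What to change.** 1. Check Protocol Version 2.0, then reconcile Protocol 9.1, 9.6 and Table 1 with SAP 4.11.1 and 4.11.3 to one rule for when a laboratory value is an AE. Declare any departure from the protocol in SAP 4.15.
2. Derive the AESI flag from the laboratory data: any post-baseline value of CTCAE grade 3 or higher, whatever its CS or NCS label. Name one CTCAE version, since Protocol 9.1 F cites v.4 and the SAP v.5.0.
3. Reconcile whether such values are SAEs, AESI or both across Protocol 9.1 F and SAP 4.11.1 and 4.11.2.
4. Show the unsolicited AE and treatment-emergent AE summary with and without isolated laboratory findings.

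The cost is wording, one derived flag and one extra table. The CTCAE grades are already planned, so no new data are needed.

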- B. Dose 1×10^{11} vp (arm 2 and arm 5)
- C. Dose 2×10^{11} vp (arm 3 and arm 6)

The injection site will be covered with a sterile dressing and the participants will stay in observation per 4 hours, in case of immediate adverse events. Investigator will decide whether the participant can leave or need additional time in hospital monitoring.

All participants will be vaccinated with the same procedure and according to the same schedule of clinical record. A standard electronic case report forms (e-CRF) will be produced and filled in.

7.2. *Medical visit*

Medical visit will be carried out at the endpoints indicated in the schedule of procedures and will always include a check of medical history, physical examination, weight and height (at screening only), pulse, blood pressure, after 10 min rest in sitting position, and body temperature.

7.3. *Blood test and other analysis for monitoring safety*

Biological testing for monitoring safety will be carried out at the endpoints indicated in the schedule of procedures at the laboratory of the clinical centers that enroll volunteers and will include:

- A. Full Blood Count
- B. Urine analysis
- C. Biochemistry: Sodium, Potassium, , , Albumin, Liver Function Tests (ALT, ALP, Bilirubin total and fractionated), Renal function (Creatinine and BUN), lactate dehydrogenases (LDH), alkaline phosphatases (ALP)
- D. Diagnostic serology: HBsAg, HCV antibodies, HIV antibodies (specific consent will be gained prior to testing blood for these blood-borne viruses)
- E. Coagulation: aPTT (ratio), PT (ratio) and INR.

Urine will be tested for pH, Glucose Protein, Haemoglobin, Leukocyte esterase, Ketones, Bilirubin, Urobilinogen and Nitrites at screening. For female participants only, urine will be tested for beta-human chorionic gonadotrophin (β -HCG) at screening.

Participants presenting with respiratory symptoms consistent with COVID-19 infection will undergo to molecular test for SARS-CoV-2 and admitted to hospital in isolation room until a negative is available.

Additional safety blood tests may be performed if clinically relevant at the discretion of the medically qualified investigators.

Item	Time of the visit since vaccination									Type of intervention
	Scr	T0	D2	W1	W2	W4	W8	W12	W24	
Window (days)	≤ 21	0	0	±1	±1	±2	±4	±7	±14	
Informed consent	x									Procedures
Eligibility	x									
Vaccination		x								
AE reporting		x	x	x	x	x	x	x	x	
Diary card		A				B				
Medical history	x									

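### Admissions that the protocol itself orders turn mild respiratory illness into SAEs under primary endpoint E, and no planned summary separates them

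*Protocol*

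**What the plan says.** **Admission.** Protocol 7.3: "Participants presenting with respiratory symptoms consistent with COVID-19 infection will undergo to molecular test for SARS-CoV-2" and be "admitted to hospital in isolation room until a negative is available". Protocol 7.8: "Participants with confirmed COVID-19 will be admitted to hospital until clearance of the infection". Neither rule has a severity threshold. For suspected cases, however, 7.8 says that people with fever and/or respiratory symptoms "will be treated according to local guideline for suspect cases of COVID-19" and does not mention admission. Protocol 15.1.3 foresees an extra visit, and testing if the investigator finds the symptoms compatible, again without mentioning admission.

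**Seriousness.** Protocol 9.1: "A SAE is an AE that results in any of the following outcomes, whether or not considered related to the study intervention". Criterion D is "Hospitalization, regardless of length of stay, even if it is a precautionary measure for continued observation". No exemption is made for admissions that the protocol requires.

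**Endpoint.** Protocol 4.2.1 E: "Occurrence of serious AE (SAE) during the whole study duration". Protocol 9.5 collects SAEs until W24. The synopsis words the same endpoint with *severe* instead of *serious*.

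**Halting.** Protocol 9.8 D: "One participant with serious adverse event considered possibly, probably or definitely related to vaccination occurs".

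**SAP.** Section 4.11.2 counts an event as serious if it requires hospitalisation. It has no precautionary clause, and it takes the seriousness flag from the eCRF. Section 4.11.1 limits the SAE lines of the overview table to treatment-emergent events, meaning those that begin or worsen within 28 days. Other SAEs appear in a listing. No table splits SAEs by the reason for admission.

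**The concern.** Seriousness normally shows how badly a participant fared. Here, for one class of illness, it shows that the protocol ordered a bed. A cough that tests negative next day and an infection with a few mild symptoms both become SAEs by criterion D. They then stand in endpoint E beside events that were life-threatening or that needed admission on clinical grounds.

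Three uses of the data are affected. First, Protocol 15.1.3 names vaccine-induced disease enhancement as a risk to be monitored. If every confirmed case is admitted and every such admission is an SAE, neither admission nor SAE status separates mild from enhanced disease. Second, Deliverable 2c compares safety between adults and elderlies. The elderly arms start later, so SAEs created by the admission rule would partly follow the respiratory illness circulating in each enrolment period. Third, sites working from the protocol and statisticians working from the SAP hold different definitions, so the same isolation stay could be flagged serious in one case and not in another.

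**Working it through.** **Step 1: the chain.**

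- An illness with respiratory symptoms is an adverse event.
- 7.3 (suspected) or 7.8 (confirmed) orders admission whatever the severity.
- 9.1 D makes an adverse event that results in admission serious, whatever the cause and even if the stay is precautionary.
- 4.2.1 E counts SAEs over the whole study.

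Each link is explicit. It is the illness that is counted; the ordered admission only upgrades it. An admission without an underlying adverse event would not count.

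**Step 2: where the texts do not line up.**

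- *Suspected cases:* 7.3 states admission; 7.8 refers to local guideline; 15.1.3 describes a visit and a test. The order for confirmed cases is not contradicted.
- *SAE definition:* 9.1 D includes precautionary admission and SAP 4.11.2 does not. Criterion F of 9.1 also makes grade 3 or higher laboratory abnormalities serious, while SAP 4.11.1 treats them as events of special interest.
- *Endpoint E:* *severe* in the synopsis, *serious* in 4.2.1.
- *Time span:* endpoint E runs to W24, but the SAP overview of SAEs covers 28 days.

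None of these texts takes the events out of the SAE count under 9.1 and 4.2.1.

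**Step 3: size.** The plan has no figure to reproduce: there is no formal sample size calculation and no expected rate of admission or SAE. The only inputs from the documents are 15 participants per arm and 6 arms (6 × 15 = 90). The probability p that a participant has an event made serious only by an ordered admission during the 24 weeks is an assumption.

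Expected number among 90 = 90p. Chance of at least one among n = 1 − (1 − p)^n. For p = 0.5% and n = 15, this is 1 − 0.995^15 = 7.2%.

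| Assumed p | Expected among 90 | At least one in an arm of 15 | At least one among 90 |
|---|---|---|---|
| 0.5% | 0.45 | 7.2% | 36.3% |
| 1% | 0.9 | 14.0% | 59.5% |
| 2% | 1.8 | 26.1% | 83.8% |
| 5% | 4.5 | 53.7% | 99.0% |
| 10% | 9 | 79.4% | above 99% |

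One such event, in a participant with no other SAE, adds 1/15 = 6.7 percentage points to an arm's SAE rate, 1/45 = 2.2 to a cohort's and 1/90 = 1.1 overall. An observed 1 of 15 has an exact 95% interval of 0.2% to 31.9%.

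The formula treats participants as independent with a common p. Clustered infections would break that. The expected counts would stay the same if p is the average, but the chances of at least one would change.

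**The case against.** The strongest reply is that criterion D is deliberate. Its wording openly over-captures, which is cautious in a first-in-human trial, and it brings every confirmed infection to the DSMB within 48 hours (Protocol 9.5). A reader might infer that these admissions should be declared non-serious. The documents do not support that as a costless repair. It would take mild confirmed infections out of the 48-hour notification and out of the reach of halting rule D, in a trial that names disease enhancement as a risk. This part of the reply stands, and the fix below leaves SAE status alone.

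Four other stronger readings also fail.

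- *Endpoint E counts a procedure.* It does not; it counts an illness whose seriousness the procedure created. Under the synopsis wording (*severe*), a mild admitted case would not count at all.
- *Every suspected case is admitted.* Protocol 7.3 reads that way for respiratory symptoms, but 7.8 and 15.1.3 do not. For fever alone, no section states admission.
- *The SAE tables are swamped and mild disease is hidden.* The SAP overview covers 28 days only, and the listings show severity, verbatim term, outcome and causality. A mild case can be found by reading the listing. What is missing is a summary that shows it.
- *Halting rules will fire and the age comparison is spoiled.* Rule D also needs at least a possible relationship to vaccination, and no probability of that can be derived. The difference in calendar time comes from sequential enrolment and affects all respiratory events; the admission rule carries it into the SAE count. No formal hypothesis test is planned.

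**Conclusion.** The point holds in a limited form. Under Protocol 7.3, 7.8, 9.1 D and 4.2.1 E taken together, a mild respiratory illness or mild infection can become an SAE solely because the protocol ordered admission, and nothing in the SAP reports such events apart. The chain is firm for confirmed COVID-19. For suspected cases it rests on 7.3, which 7.8 and 15.1.3 do not match. It also rests on the 4.2.1 wording of endpoint E and not on the synopsis.

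The size depends on a rate that the documents do not give. At the low end of the assumed range such events may not occur at all (0.45 expected among 90); at the high end there would be about nine. With 15 per arm, a single one is enough to alter how an arm's SAE rate reads. The effect is on the interpretation of a primary safety endpoint. It does not show that safety reporting is inadequate. The change is worth making because it is cheap and loses no safety information.

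**What to change.** 1. Keep these events as SAEs. Leave the 48-hour DSMB notification, the halting rules and the admission rules as they are.
2. Add one eCRF field on the SAE record for the reason for admission: isolation required by 7.3 or 7.8, or the participant's condition.
3. In SAP 4.11.1 and 4.11.2, tabulate SAEs by arm over the whole 24 weeks in two rows: serious only through a protocol-required admission, and meeting any other seriousness criterion. Admission needed for the participant's condition belongs in the second row. The 28-day overview can stay beside it.
4. Have the sponsor reconcile three sets of text: the admission wording in Protocol 7.3, 7.8 and 15.1.3; the SAE definitions in Protocol 9.1 and SAP 4.11.2; and the endpoint E wording in the synopsis and 4.2.1. Which admission rule applies is a clinical decision and is not proposed here.

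The cost is one eCRF field, one extra table row and some wording. Sites must judge the reason for admission, and some cases will be borderline. Because every event stays an SAE, a wrong judgement moves it between rows and does not remove it.
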